11.0 DATA COLLECTION, STUDY MONITORING, AND CONFIDENTIALITY

11.1 Enrollment on Study

Confirm subject eligibility as defined in Section 4.0 Patient Eligibility. Complete and sign the 'Patient Eligibility Checklist.' Be sure that all required values and dates are filled in.

Fax the completed Checklist to the Central Protocol and Data Monitoring Office (CPDMO) at Follow with a phone call to form to ensure that the fax has been received. Eligibility will be reviewed, a patient-specific consent form will be generated, and the consent, protocol, and protocol standard order set will be delivered to the area designated on the Checklist. The signed consent form must be faxed to the CPDMO in order to complete the enrollment.

The CPDMO is staffed 7:30 am-6:00 pm CST, Monday through Friday (excluding holidays) and 9:00 am to 1:00 pm on Saturday. The office is staffed 9:00 am to 3:00 pm CST all weekday holidays except Christmas. A staff member is available by pager Saturday afternoons, Sundays and on Christmas Day for SJCRH enrollments.

11.2 Data Collection

Case report forms (CRFs) will be completed and reviewed by the SJCRH data manager for accuracy and completeness. Data will then be entered into a secure CRIS database.

11.3 Study Monitoring

Source document verification of eligibility and informed consent for 100% of St. Jude participants will be performed by the Eligibility Coordinators within 10 working days of completion of enrollment.

The Clinical Research Monitor will perform monitoring of applicable essential regulatory documentation. Also, reviewing for the timeliness of serious adverse event reporting (type, grade, attribution, duration, timeliness and appropriateness) for selected study participants *semi-annually* and track accrual continuously. The monitor will verify those data points relating to the primary study objective for a certain number of study enrollees as specified in the Moderate Risk monitoring plan checklist for this study. Protocol compliance monitoring will include participant status, safety assessments, eligibility, the informed consent process, participant protocol status, off-study, and off-therapy criteria. The Monitor will generate a formal report which is shared with the Principal Investigator (PI), study team and the Internal Monitoring Committee (IMC).

Monitoring may be conducted more frequently if deemed necessary by the CPDMO or the IMC.

Continuing reviews by the IRB and CT-SRC will occur at least annually. In addition, SAE reports in TRACKS (Total Research and Knowledge System) are reviewed in a timely manner by the IRB/ OHSP.

11.4 Confidentiality

Study numbers will be used in place of an identifier such as a medical record number. No research participant names will be recorded on the data collection forms. The list containing the study number and the medical record number will be maintained in a locked file and will be destroyed after all data have been analyzed.

The medical records of study participants may be reviewed by the St. Jude IRB, FDA, clinical research monitors, etc.

12.0 Statistical Considerations

12.1 To estimate the rates of local failure and tumor progression

The primary objective is to estimate the local control and patterns of failure for patients with primary musculoskeletal tumors including the Ewing's sarcoma family of tumors (ESFT), rhabdomyosarcoma (RMS) and non-rhabdomyosarcoma soft tissue sarcoma (STS) treated with image guided three-dimensional conformal radiation therapy. Different tumor types are accessioned to this study and their local failure rates differ significantly. To account for these differences, three groups of patients will be selected for local failure analysis based on the expected accrual of these patients to this study (Appendix E). These groups are defined by histology, site and degree of surgical resection and are selected to allow meaningful comparison with targeted rates of local control. Target local control rates for these specific treatment groups are established and listed in appendix E based on selected literature (3, 5-6, 9-12, 64,65). A lower limit to the local control rate is given to define a threshold below which the paradigm for treatment described in this protocol is deemed unacceptable. Analysis of local control will be undertaken for a treatment group at each event

Rev 5.2, dated: 6/9/2023 Protocol document date: 6/9/2023

counted as a local failure, when each treatment group has completed accrual and has been followed for five years, and at intervals specified below. The accrual of patients in five years in the study for all tumor types is projected in Table 12.1.1 below. For the local control analysis, projections for accrual for the specific treatment groups are listed in Table 12.1.2 below. For nonsequential tests, if the actual final accruals are different from the projected accruals, then for Group III RMS or for the Resected or Small ESFT (target 85%), the lower limit to the local control rate is 60%, 70%, 72%, or 73.3%, respectively, for the final accrual of 15, 20, 25, or 30 patients. For the Resected STS (target rate 90%), the lower limit 73.3%, 75%, 76%, or 80%, respectively, for the final accrual of 15, 20, 25, or 30 patients. For the Large ESFT (target rate 55%), the lower limit 33.3%, 35%, 36%, or 40%, respectively, for the final accrual of 15, 20, 25, or 30 patients. A sequential safety-monitoring plan is given in Table 12.1.3 in terms of minimum number for the number of patients locally controlled corresponding to the number of patients accrued within a treatment group during the study, assuming the final accrual is 30 patients in each treatment group. The minimum number is calculated for each of the four treatment groups (Group III RMS, Resected STS, and Resected / Small ESFT, and Large ESFT), respectively. For each of the four treatment groups, when the number of patients accrued during the study reaches 5, 10, 15, 20, 25, or 30, the number of patients with local tumor control will be reviewed and must not be less than the corresponding minimum number (Table 12.1.3). If fewer patients than targeted are controlled locally, then the rate of local control is considered be too low for that treatment group and the study for that treatment group will be stopped for investigating the reasons. At any event counted as a local failure during study, the local control rate for that treatment group will be determined. If the local control rate is lower than targeted, then accrual to that treatment group will be halted and the reasons investigated. If the number of patients accrued is other than 5, 10, 20, 25, or 30, the assistance of the statistician ([name].) may be requested by the PI ([name]) to calculate the new minimum number of patients locally controlled according to the actual number of patients accrued. In the above monitoring scheme, the number of patients locally controlled is counted disregarding the timing (since initiation of radiation therapy) of events (local failures) as this calculation is based on a target rate of local control at 2 years that is identical at 5 years. These target rates are expected estimates of local control and not actual local control rates based directly on historic data. We will use the survival model with competing risk (e.g., patient death) (57) to estimate the rates of local failure and tumor progression (defined in 10.1-10.6) for each tumor group. One-hundred evaluable patients will be required based on the projected accruals in table 12.1.1 below. We expect to enroll a total of 110 patients based on our current accrual to generate 100 evaluable patients for analysis.

Table 12.1.1 Projected Accruals

	RMS	STS	ESFT
W/o Metastases	18	26	26
W & w/o Metastases	29	26	37

Table 12.1.2 Accrual in Groups for Local Control Analysis

	Group III RMS	Resected STS	Resected ESFT or Small (<8cm) ESFT	Large (≥8cm) ESFT
W/o Metastases	17	24	15	3
W & w/o Metastases	28	24	18	12

Table 12.1.3

Safety Monitoring Plan: Minimum number of patients locally controlled per patients enrolled in each treatment group*

	Minimum Expected Number of Patients with Local Tumor Control								
Number of			Resected ESFT						
Patients Enrolled	Group III	Resected	or						
in a Treatment	RMS	STS	Small (<8cm)	Large (≥8cm) ESFT					
Group			ESFT						
5	3	3	3						
10	7	7	7	1					
15	10	11	10	3					
20	13	15	13	4					
25	16	19	16	7					
30	19	22	19	11					

*For each of the three treatment groups, when the number of patients accrued during the study reaches 5, 10, 15, 20, 25, or 30, if the number of patients locally controlled is equal to or less than the corresponding minimum number, then the rate of local control is considered be too low for that treatment group and the study for that group will be stopped for investigating reasons.

The Second Phase Accrual: The original plan of accrual of 110 patients has been completed (September 2007), and additional accrual of patients is planned for this study as the second phase of accrual. The numbers of patients anticipated for the four treatment groups for the second phase accrual are shown in Table 12.1.4. These numbers are estimated based on the accrual of an additional 100 patients with the same distribution of disease (histology, size and use of surgery) as the initial 110 patient cases. For the groups of ESFT-small/resected and ESFT-large, the treatments in the second phase are exactly the same as that in the first phase, so the patients in the second phase will be taking together with those in the first phase for safety monitoring according to the plan in Table 12.1.3. The treatments for the groups of Group III RMS and Resected STS will be changed such that the irradiation margin will be decreased from 2cm to 1.5cm for the Group III RMS, and be decreased from 1.5cm to 1.0cm for the Resected STS. Since the patients in the second phase in these two groups may be at higher risk for local failure than those in the first phase (due to clinical treatment margin reduction), these patients will be monitored separately from, as well as together with, the patients from the first phase. The monitoring plans for these two groups are given in Table 12.1.5. For each group, the accrual of patients will be held if the stopping rule is activated by any one of the two monitoring plans for the aroup.

Table 12.1.4	
The Second Phase Accrual in Groups for Local Control Analysis	

	Group III RMS	Resected STS	Resected ESFT or Small (<8cm) ESFT	Large (≥8cm) ESFT
W & w/o Metastases	35	35	13	12

For Group III RMS or for the Resected or Small ESFT (target 85%), the 5% lower limit for non-sequential tests for the local control rate is 26 (74.3%) or 50 (76.9%), respectively, for the final accrual of 35 or 65 patients. For the Resected STS (target rate 90%), the 5% lower limit is 28 (80.0%) or 54 (83.1%), respectively, for the final accrual of 35 or 65 patients. From the sample sizes of the fixed sample test design, we derived the sequential boundaries in Table 12.1.5 for monitoring the local control rates.

Table 12.1.5

The Second Phase Safety Monitoring Plan: Minimum number of patients locally controlled per patients enrolled in each treatment group*

	Minimum Expected Number of Patients with Local Tumor Control					
Number of Patients Enrolled	Group I	II RMS	Resecte	ed STS		
in a Treatment Group	2 nd Phase Only	Two Phases Together	2 nd Phase Only	Two Phases Together		
5	2		2			
10	5		6			
15	9		10			
20	12		14			
25	16		18			
30	20		22			
35	25		27			
40		28		31		
45		32		35		
50		36		39		
55		40		44		
60		44		48		
65		49		53		

*For the second phase accrual for each of the two treatment groups, the local controls will be monitored simultaneously in two ways: 1) alone: when the number of patients accrued from the second phase accrual reaches 5, 10, 15, 20, 25, or 35, if the number of patients locally controlled is equal to or less than the corresponding minimum number, then the rate of local control is considered be too low for that treatment group and the study for that group will be stopped for investigating reasons; 2) together with patients accrued in the first phase: during the second phase accrual, if the number of all patients accrued so far from the two phases reaches 40, 45, 50, 55, 60, or 65 and if the number of patients locally controlled is equal to or less than the corresponding minimum number, then the rate of local control is considered be too low for that study for that group will be stopped for investigating minimum number, then the rate of local control is considered be too and if the number of patients locally controlled is equal to or less than the corresponding minimum number, then the rate of local control is considered be too low for that treatment group and the study for that group will be stopped for investigating reasons.

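### Section 12.1 and the footnote to Table 12.1.3 set stopping boundaries one patient apart at every look, and two of the non-sequential lower limits are out of line with the rest

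*Combined protocol and SAP*

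**What the plan says.** **Sequential boundary.** Section 12.1 presents Table 12.1.3 as a safety-monitoring plan, "assuming the final accrual is 30 patients in each treatment group". At 5, 10, 15, 20, 25 and 30 patients the number locally controlled "must not be less than the corresponding minimum number (Table 12.1.3". The footnote to the same table stops the group "if the number of patients locally controlled is equal to or less than the corresponding minimum number". In the second phase, Section 12.1 keeps Table 12.1.3 for the two ESFT groups and moves Group III RMS and resected STS to Table 12.1.5.

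**Per-failure rule.** Section 12.1 also has the group's local control rate determined at every local failure, and halts accrual if that rate is lower than targeted.

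**Non-sequential limits.** Section 12.1 gives the purpose: "A lower limit to the local control rate is given to define a threshold below which the paradigm for treatment described in this protocol" is unacceptable. At an 85% target, for final accruals of 15, 20, 25 or 30, "the lower limit to the local control rate is 60%, 70%, 72%, or 73.3%, respectively". Further: "For the Large ESFT (target rate 55%), the lower limit 33.3%, 35%, 36%, or 40%, respectively". Appendix D gives limits at the projected accruals: 71.4% (n=28), 75% (n=24), 66.7% (n=18) and 35% (large ESFT, n=12). A level appears only in the second-phase text: "the 5% lower limit for non-sequential tests for the local control rate is 26 (74.3%) or 50 (76.9%), respectively" for 35 or 65 patients. That sentence covers Group III RMS and resected or small ESFT together.

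**The concern.** One table cannot carry two boundary rules. With 3 of the first 5 patients controlled in a group with an 85% target, the body text lets the group continue and the footnote stops it. Section 14.0 leaves monitoring of local control to the principal investigator without DSMB review, so the written rule is what governs.

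The non-sequential limits decide whether a treatment paradigm is judged unacceptable. Apart from the second-phase entries they come with no level, and no formula is given for any of them. An entry that departs from the rest therefore cannot be told apart from a slip.

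**Working it through.** **Inputs.** Targets are 85%, 90%, 85% and 55% (Appendix D). Table 12.1.3 minimums at 5, 10, 15, 20, 25, 30 patients are 3, 7, 10, 13, 16, 19 (Group III RMS, and resected or small ESFT); 3, 7, 11, 15, 19, 22 (resected STS); and 1, 3, 4, 7, 11 from n=10 (large ESFT, no entry at 5). X, the number controlled, is binomial at the target rate. Every patient's final status is taken as known at the look.

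**1. First look, 85% target.** P(X=0), …, P(X=3) of 5 are 0.0001, 0.0022, 0.0244 and 0.1382.
- Stop only below 3: P(X≤2) = 0.0266.
- Stop at or below 3: 0.0266 + 0.1382 = 0.1648.

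**2. All looks.** Carry forward the distribution of X among groups not yet stopped, add a binomial(5, p) count between looks (10 for the first large ESFT look), and remove the counts that stop. Cumulative chance of stopping at target, below / at or below the minimum:

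| Look | 85% | 90% | 55% |
|---|---|---|---|
| 5 | 2.7% / 16.5% | 0.9% / 8.1% | none |
| 10 | 6.1% / 24.1% | 1.8% / 11.3% | 0.03% / 0.45% |
| 15 | 6.5% / 24.8% | 2.4% / 12.9% | 0.13% / 0.89% |
| 20 | 6.5% / 24.9% | 2.8% / 13.8% | 0.14% / 0.92% |
| 25 | 6.6% / 24.9% | 3.0% / 14.3% | 0.26% / 1.27% |
| 30 | 6.6% / 24.9% | 3.1% / 14.3% | 1.5% / 3.8% |

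Projected pooled accrual is 12 + 12 = 24 for large ESFT, so its last expected look is n=20: 0.1% against 0.9%. For resected or small ESFT it is 18 + 13 = 31, which reaches every look.

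**3. Non-sequential limits as counts.** Nineteen of the 20 are whole counts. At target they flag 0.4% to 3.3% if only lower counts are flagged, and 1.7% to 7.7% if equality is flagged too.

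The exception is large ESFT at n=12. Here 0.35 × 12 = 4.2, and 4/12 = 33.3% < 35% < 5/12 = 41.7%. Either direction therefore flags 4 or fewer: P(X≤4) = 0.1117 at 55%, against P(X≤3) = 0.0356. The 35% is also the Section 12.1 entry for n=20 (7/20); the documents do not say whether it was carried over.

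**4. The 85% row.**

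| Limit | Below | At or below |
|---|---|---|
| 9/15 | 0.4% | 1.7% |
| 14/20 | 2.2% | 6.7% |
| 18/25 | 2.6% | 7.0% |
| 22/30 | 2.8% | 7.0% |

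At n=15, 10 or fewer has probability 6.2%, close to the other three. So 9/15 is one low relative to its neighbours, or each of them is one high relative to it.

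**5. Is there a common rule?** Of the 19 whole-count limits, the largest k with P(X≤k) ≤ 5% reproduces 7, the 5th percentile 12, and the tail nearest 5% 16. A cut-off of P(X≤k) ≤ 8%, fitted after the fact, reproduces 18 and misses only 9/15.

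**6. Direction.** Section 12.1 says: "From the sample sizes of the fixed sample test design, we derived the sequential boundaries in Table 12.1.5". The last rows of that table (25, 49, 27, 53, stopping at or below) flag the same counts as its fixed limits (26/35, 50/65, 28/35, 54/65) read as strictly below. This agrees with the stated purpose of the limits but does not settle the direction for the other entries.

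**The case against.** A reader might infer that the footnote gives the plan a 25% false-stop rate. The documents do not support that. The per-failure rule acts as well and, read literally, dominates. At an 85% target any failure among the first six patients leaves at most 5/6 = 83.3%, so the chance of a halt by n=5 is 1 − 0.85^5 = 56% at a true rate of 85%. The same recursion, applied patient by patient, gives 81% by n=30. If a different target was meant there, the text does not say so. The figures above therefore describe Table 12.1.3 alone.

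Much of the effect is also historical. First-phase accrual finished in September 2007, and RMS and STS then moved to Table 12.1.5. Even for resected or small ESFT, 18 first-phase patients were projected, so the looks to n=15 belong mainly to the first phase. Looks 20 to 30 add only 24.94 − 24.76 = 0.18 points at or below the minimum, and 6.58 − 6.46 = 0.12 points below it. This stands. It narrows the consequence but does not remove the contradiction, which is in current text.

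A reader might also infer that the limits are arbitrary and all 20 need replacing. That goes too far. Read as below, the direction in the stated purpose, none of the 19 whole-count limits flags more than 3.3%. One unstated cut-off fits 18 of them, and 9/15 errs towards fewer false flags and itself meets P(X≤k) ≤ 5%. No 5% level is attached to the first-phase or Appendix D limits. An unattainable percentage can still be applied: at the pooled 24 patients, below 35% means 8 or fewer, 2.7% at target. What survives is that the n=12 entry departs from all the others in either direction, and that 9/15 does not fit its own row.

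**Conclusion.** The contradiction over Table 12.1.3 is real and is the main point. It is one patient at every look, worth 6.6% against 24.9% (85% target), 3.1% against 14.3% (90%) and 1.5% against 3.8% (55%) in the chance of ever stopping at target over looks to n=30. For large ESFT at its projected pooled accrual it is 0.1% against 0.9%. These figures assume binomial outcomes at the target rate and final status known at each look; they are lower if recently enrolled patients count as controlled. They exclude the per-failure rule. In the second phase they bear only on the two ESFT groups; the RMS and STS figures concern the completed first phase.

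Two narrower points also hold: 35% at n=12 flags 11.2% at target under either direction, and 9/15 at 85% is one patient out of line with its row. The documents do not show how either arose. The second-phase limits, including 26/35 and 50/65 for both Group III RMS and resected or small ESFT, are mutually consistent and not in question. This review does not say which stopping boundary is right.

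**What to change.** 1. Reconcile Section 12.1 and the footnote so that Table 12.1.3 has one boundary rule. Report the resulting chance of stopping at target, saying that it excludes the per-failure rule.
2. State the level and direction used for the non-sequential limits. Check the n=12 large ESFT and n=15 (85%) entries against that rule, and print them as counts.
3. If 5% is confirmed, the n=12 limit should flag 3 or fewer (3.6% at target). Leave the other limits alone unless the confirmed rule requires a change.
4. Date any revision and keep the earlier limits on record, since Section 2.1 already cites two-year local control results from this trial.

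The editing cost is one aligned wording, one sentence on level and direction, and two entries to check. The statistical cost falls at n=12: flagging 3 or fewer instead of 4 or fewer lowers the chance of flagging a true rate of 40% (assumed) from 44% to 23%. Over an assumed range of true rates from 45% to 35%, that chance goes from 30%–58% to 13%–35%.

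### Table 12.1.3: the text of Section 12.1 lets a group continue when the number controlled equals the minimum, the table's footnote stops it, and no error rate is stated under either reading

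*Combined protocol and SAP*

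**What the plan says.** Section 12.1 reviews each treatment group at 5, 10, 15, 20, 25 and 30 patients against the minimum counts in Table 12.1.3. The body text says that "the number of patients with local tumor control will be reviewed and must not be less than the corresponding minimum number (Table 12.1.3"), and it gives the trigger as "If fewer patients than targeted are controlled locally". The footnote to the table stops a group "if the number of patients locally controlled is equal to or less than the corresponding minimum number".

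The two texts also differ on scope. The body says "The minimum number is calculated for each of the four treatment groups", and the table has four columns. The footnote opens with "For each of the three treatment groups".

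A further check applies at every local failure: "If the local control rate is lower than targeted, then accrual to that treatment group will be halted and the reasons investigated". For patient counts between looks, the text says only that the statistician may be asked for a new minimum.

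Table 12.1.3 is still in use. For the second phase, Section 12.1 says that patients in the two ESFT groups "will be taking together with those in the first phase for safety monitoring according to the plan in Table 12.1.3". Group III RMS and Resected STS move to Table 12.1.5 for second-phase monitoring.

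Section 14.0 says there is no DSMB referral and has the principal investigator monitor local control from Table 12.1.2. That table lists projected accrual and holds no minimum counts.

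**The concern.** Both texts are current, and they give opposite instructions at a tie. With 3 of 5 or 7 of 10 controlled in an 85% group, the body text continues accrual and the footnote stops it. This is the rule by which the investigator, without a DSMB, judges local control to be too low. Two careful readers would act differently on the same count.

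A stated error rate would show which rule was meant, but Section 12.1 gives none for this table. Its only stated level is the 5% attached to the non-sequential limits at 35 and 65 patients in the second phase. Those limits lead to Table 12.1.5, not to Table 12.1.3.

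**Working it through.** **Inputs.** Target rates (Section 12.1): 85% for Group III RMS and for Resected/Small ESFT, 90% for Resected STS, 55% for Large ESFT. Lower-limit rates (Appendix D): 71.4% RMS, 75% STS, 66.7% Resected/Small ESFT, 35% Large ESFT. Minimum counts m at n = 5, 10, 15, 20, 25, 30 (Table 12.1.3):

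- Group III RMS and Resected/Small ESFT: 3, 7, 10, 13, 16, 19
- Resected STS: 3, 7, 11, 15, 19, 22
- Large ESFT: no entry at 5, then 1, 3, 4, 7, 11

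**Step 1. Reproduce the plan's only stated level.** Take the 5% limit as the smallest k with P(X ≤ k) ≥ 0.05, X binomial.

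- 85%, n = 35: P(X ≤ 25) = 0.029, P(X ≤ 26) = 0.069, limit 26
- 85%, n = 65: P(X ≤ 49) = 0.028, P(X ≤ 50) = 0.055, limit 50
- 90%, n = 35: P(X ≤ 27) = 0.020, P(X ≤ 28) = 0.055, limit 28
- 90%, n = 65: P(X ≤ 53) = 0.026, P(X ≤ 54) = 0.057, limit 54

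All four match Section 12.1. They are fixed-sample limits, so they supply no error rate for Table 12.1.3.

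**Step 2. One look by hand.** For an 85% group at n = 5, m = 3:

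- Body text (stop if X < 3): P(X ≤ 2) = 0.0001 + 0.0022 + 0.0244, which is 0.0266 before rounding of the terms.
- Footnote (stop if X ≤ 3): add P(X = 3) = 10 × 0.85³ × 0.15² = 0.1382, giving 0.1648.

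**Step 3. All looks.** I used an exact recursion. Carry the distribution of the number controlled among groups not yet stopped, add a binomial count for the next patients (five at a time; ten to the first Large ESFT look), remove the mass with X < m (or X ≤ m), and accumulate what is removed. Every patient's final status is taken as known at each look.

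Probability of having stopped by n = 30:

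| Group | Rate | Body text (<) | Footnote (≤) |
|---|---|---|---|
| RMS; Resected/Small ESFT | target 85% | 6.6% | 24.9% |
| Resected STS | target 90% | 3.1% | 14.3% |
| Large ESFT | target 55% | 1.5% | 3.8% |
| Group III RMS | lower limit 71.4% | 41.7% | 69.2% |
| Resected STS | lower limit 75% | 54.2% | 76.3% |
| Resected/Small ESFT | lower limit 66.7% | 58.6% | 81.5% |
| Large ESFT | lower limit 35% | 51.1% | 66.3% |

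**Step 4. Where the gap arises.** Cumulative stopping probability in an 85% group on target:

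| n | < | ≤ | Gap |
|---|---|---|---|
| 5 | 0.0266 | 0.1648 | 0.1382 |
| 10 | 0.0608 | 0.2411 | 0.1803 |
| 30 | 0.0658 | 0.2494 | 0.1836 |

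By n = 10 the gap is 0.1803 of 0.1836, or 98%. The four later looks add about 0.3 points.

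**The case against.** The strongest reply is that little now turns on this. Section 12.1 counts patients as controlled without regard to timing, so recent enrolees count as controlled and early looks rarely trigger. The first phase completed accrual in September 2007. RMS and STS in the second phase have their own table, and a trigger is a hold to investigate reasons. The three-versus-four slip and the Section 14.0 reference are editorial. A table of stopping probabilities is good practice, and its absence alone is not an error. All of this stands and limits the weight of the point. It does not remove the contradiction at a tie.

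Three stronger readings are tempting but unsupported.

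- **That the entries reveal the intended rule.** A reader might compare Tables 12.1.3 and 12.1.5. The Resected STS entries are one lower in Table 12.1.5 from n = 5 to 25, but both are 22 at n = 30. The RMS entries differ by −1, −2, −1, −1, 0 and +1. The second-phase columns run to 35 patients, while Table 12.1.3 assumes 30, so a shift need not reflect the operator. Table 12.1.5 agrees with its own footnote and is not in question.
- **That the per-failure check halts a group whenever its observed rate is below the target rate.** That sentence directly follows the minimum-count rule, and the table minimum is the more natural threshold. The sentence does not say so, and the documents give no rule for minima between looks, so I put no figure on what this check adds.
- **That the remaining exposure can be read from projected accrual.** Table 12.1.2 projects 28, 24, 18 and 12 patients. The second-phase text scales 35, 35, 13 and 12 per 100 from the first 110 cases, which implies about 38, 38, 14 and 13. The two do not agree, so the last look reached in each group is uncertain.

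**Conclusion.** The point holds as a minor one. The body text and the footnote to Table 12.1.3 disagree when the count equals the minimum, and no error rate is given for either rule. With all outcomes known, the operator moves the on-target stopping probability by n = 30 from 6.6% to 24.9% in the 85% groups, with smaller shifts elsewhere. It moves detection at the lower-limit rates by about 15 to 28 points (66.3 − 51.1 = 15.2 for Large ESFT; 69.2 − 41.7 = 27.5 for RMS).

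The figures assume independent patients with a common rate, 30 patients per group as Table 12.1.3 does, and the table looks alone. Unseen failures raise the count controlled at a look, so the on-target figures are upper bounds, and detection is overstated in the same way.

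A reader might infer that a group meeting its target now faces a one-in-four chance of being stopped. The documents do not support that. In the 85% groups nearly all of the difference lies at 5 and 10 patients, and those looks should be past. The remaining effect is small. It falls mainly on the two ESFT groups, and on any report that must say which rule was applied.

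**What to change.** - Reconcile the body of Section 12.1 and the footnote to one comparison operator for Table 12.1.3, state that it covers all four groups, and confirm that the entries were derived under it. The sponsor chooses the boundary. Table 12.1.5 and its footnote need no change.
- Report, for each group, the stopping probability at the target and lower-limit rates under the chosen rule, with the assumption made about outcomes not yet known.
- State which threshold the per-failure check uses. If it is the table minimum, say how minima between looks are set.
- Point Section 14.0 to the monitoring tables (12.1.3 and 12.1.5).
- In reports, say which rule was applied at looks already taken.

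The cost is wording in Sections 12.1 and 14.0 and one short table. It needs no patients and no new data.
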